8 ETHICAL AND REGULATORY CONSIDERATIONS

8.1 Assessment and management of risk

While undertaking observations of ward staff delivering care, the delivery of an unacceptable standard of clinical practice may become apparent or be strongly suspected by the researcher (JH), who does not hold a clinical qualification. If this occurs, the researcher (JH) will discuss these concerns with the nurse in charge of the ward. Furthermore, the one-to-one conversations as part of fieldwork may reveal disclosures that require action. We do not expect these situations to occur frequently but acknowledge that they are possible. Information sheets include a disclaimer that the researcher has a duty to report harmful or abusive care practices. This will be discussed with those taking part before data collection begins. The researcher will have completed courses in Safeguarding Adults (Levels 1 and 2) prior to commencement of this study. Should participant disclosures or observations of care reveal criminal acts, including acts of abuse or neglect, appropriate safeguarding procedures will be immediately followed.

We recognise the possible effects of Covid-19, and other infections on the execution of the research:

- The proposed research relies on direct access to wards, and we will follow local regulations to access required (e.g. masking, use of LFTs before entering wards)
- The ethnographic observations require a physical presence of only 1 team member (JH).
 Permissions and governance will be prioritised early (see gantt chart)
- Sampling and data collection is designed to require only limited support from NHS systems and frontline resources and is informed by ongoing discussions with our collaborators
- Remote working can be used when required for some project communication, PPI Advisory Group and Project Steering Group meetings
- The project prioritises the delivery of open access outputs, and the team have expertise in delivering blended learning and online resources where preferred

8.2 Research Ethics Committee (REC) and other Regulatory review & reports

Before the start of the study we will seek ethics committee approval through the HRA process and through a Mental Capacity Act trained NHS REC. Both KF and JH have expertise in obtaining REC (15/WA/0191,18/WA/0033, IRAS 313816) approval to involve vulnerable populations in research in hospital settings and the application of the Mental Capacity Act (2005).

Substantial amendments that require review by NHS REC will not be implemented until that review is in place and other mechanisms are in place to implement at site. All correspondence with the REC will be retained. The Chief Investigator (JH) will produce the annual reports as required and notify the REC of the end of the study. An annual progress report (APR) will be submitted to the REC within 30 days of the anniversary date on which the favourable opinion was given, and annually until the study is declared ended. If the study is ended prematurely, the Chief Investigator will notify the REC, including the reasons for the premature termination. Within one year after the end of the study, the Chief Investigator will submit a final report with the results, including any publications/abstracts, to the REC.

Regulatory Review & Compliance

Before any site can enrol patients into the study, the Chief Investigator/Principal Investigator will ensure that appropriate approvals from participating organisations are in place – specifically site agreements with the two hospitals where recruitment and data collection will take place.

For any amendment to the study, the Chief Investigator, in agreement with the sponsor will submit information to the appropriate body in order for them to issue approval for the amendment. The Chief Investigator will work with sites (R&D departments at NHS sites as well as the study delivery team) so they can put the necessary arrangements in place to implement the amendment to confirm their support for the study as <a href="mailto:amended:am

Amendments

If the sponsor wishes to make a substantial amendment to the REC application or the supporting documents, the sponsor must submit a valid notice of amendment to the REC for consideration with the express agreement and cooperation of the Chief Investigator (JH) using the process described below. The REC will provide a response regarding the amendment within 35 days of receipt of the notice. It is the sponsor's responsibility to decide whether an amendment is substantial or non-substantial for the purposes of submission to the REC.

Amendments also need to be notified to the national coordinating function of the UK country where the lead NHS R&D office is based and communicated to the participating organisations (R&D office and local research team) departments of participating sites to assess whether the amendment affects the NHS permission for that site. Note that some amendments that may be considered to be non-substantial for the purposes of REC still need to be notified to NHS R&D (e.g. a change to the funding arrangements).

- The process for making amendments is that the sponsor should discuss any wishes to make substantial amendents with the Chief Investigator (JH)
- Substantive changes will be communicated by the Chief Investigator (JH) to relevant stakeholders (e.g., REC, R&D, regulatory agencies).
- The amendment history will be tracked in the site files, with protocol version numbers showing the most recent protocol version and previous protocol(s) archived and marked as outdated in the title.

8.3 Peer review

The details provided in this protocol were reviewed as part of the NIHR RfPB grant submission process.

8.4 Patient & Public Involvement

This proposal has been developed in collaboration with people with learning disabilities and their carers. One of our co-applicants has lived experience of having a learning disability (MB) and another of our co-applicants is a parent of a woman with a learning disability (AI). This has informed the research focus and the methods we are using that supports the inclusion of people with severe and profound learning disabilities, and our approach to co-production. This includes the use of EasyRead, Photosymbols, Widgit symbols, simple language, providing questions ahead of time, use of graphics, role play scenarios and stories, embedded throughout the design of this study and in the PPI work.

A summary of PPI activities

• Our co-applicants MB and AI will meet with the other co-applicants monthly except during fieldwork when there will be no meetings

Months 1-3 JH will identify and spend a total of two days with somebody with profound and multiple learning disabilities and their carer(s), learning how they communicate including assent, dissent and distress. This will inform the research protocol and co-design outputs.

The PPI Advisory Groups with people with learning disabilities will meet monthly (except during fieldwork) to ensure they are fully involved. This ensures they will have adequate time to be fully involved in the research design, implementation, analysis, and output development. We will meet with the carers' group every two months as their availability and support needs will be lower.

Activities will be:

- · Month 1: Agree terms and support required
- Month 2: Agree key principles for recruitment and accessible project materials
- Months 3-4: Test and critique accessible materials
- Months 5-6: Discuss responses to REC, develop toolkit for accessible interviews
- Month 9: Discuss initial findings and develop third order coding
- Months 9-17: co-design sessions to create outputs

JH and FL will support a PPI member with a learning disability to develop and present research findings at a conference (preference given to MB).

We will hold a series of workshops with our advisory groups of people with learning disabilities, carers and families. The workshops will discuss and 'member check' initial findings (100) and co-design and develop guidance and study outputs, using initial findings from the data.

We will adapt Accelerated Experience-Based Co-Design (106) significantly in response to critiques about its use with people with learning disabilities and other vulnerable groups (57,58) for instance in using a set of principles derived from the approach rather than a series of rigid steps (58). We will also adapt these methods for the specific communication preferences, cognitive needs, and expertise of the people with learning disabilities in our advisory groups (54,107–110), using our 'toolbox of adapted and augmentative supports' and role play scenarios, developing this approach with our PPI representatives and PPI lead.

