The role of the Steering Committee is to provide overall supervision for a project on behalf of the study's Sponsor and Funder and to ensure that it is conducted to the rigorous standards set out in the UK Policy Framework for Health and Social Care and the Guidelines for Good Clinical Practice.

The role of the Study Steering Committee is as follows:

- To provide advice, through its Chair, to the study's funder, sponsor, Chief Investigator, host institution, and contractor
- To concentrate on the study's progress, adherence to the protocol, and patient safety (where appropriate), and to consider new information of relevance to the research question

- To uphold the rights, safety and well-being of the participants: these are the most important considerations and should prevail over the interests of the research
- To ensure appropriate ethical and other approvals are obtained in line with the project plan
- To agree proposals for substantial protocol amendments and provide advice to the sponsor and funder regarding approvals of such amendments
- · To provide advice to the investigators on all aspects of the study

PPI advisory groups: Our PPI Advisory Groups of people with learning disabilities (Treat Me Well at Southampton Mencap and Southern Health's Patient Experience group) and carers are already established. Representatives (a person with a learning disability and a family carer) from the above Advisory Groups are co-applicants. The lead researcher has spent two days with a public contributor with a profound learning disability to learn about how this person communicates, their needs and what is important to them, which has been used to inform how involvement in our research could be improved for people with profound learning disabilities. We are paying for PPI contributors' time using NIHR PPIE rates.

A summary of PPI activities

- MB and AI will meet with the other co-applicants monthly except during the fieldwork phase (March-June 2025)
- Months 1-3 JH will identify and spend a total of two days with a person with profound and multiple learning disabilities and their carer(s), learning how they communicate including assent, dissent and distress.
- The PPI Advisory Groups with people with learning disabilities will meet monthly (except during
 the first two months of fieldwork) to ensure they are fully involved. This ensures they will have

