 adequate time to be fully involved in the research design, implementation, analysis, and output
 development. We will meet with the carers' group every two months as their availability and
 support needs will be lower. Activities will be:
- Month 1: Agree terms and support required
- Month 2: Agree key principles for recruitment and accessible project materials
- Month 3-4: Test and critique accessible materials created by FL (PPI Lead)
- Months 5-6: Discuss responses to REC, develop toolkit for accessible interviews
- Month 9: Discuss initial findings and develop third order coding
- Months 9-18: co-design sessions to create outputs

JH and FL will support a PPI member with a learning disability to develop and present research findings at a conference (preference given to MB).

PROTOCOL CONTRIBUTORS

The Sponsor (University Hospital Southampton NHS Foundation Trust (UHS) is the organisation that is taking legal responsibility for the research study.

The funder NIHR has carried out a peer review of the study prior to awarding funding. All requirements of an NIHR contract will be met, including provision of 6 month progress reports and the delivery of progress milestones as required.

The PI (JH) is responsible for the design, conduct, data analysis and interpretation, manuscript writing, and dissemination of results.

This protocol has been developed in collaboration with people with learning disabilities and their carers. This includes the Treat Me Well group (Southampton Mencap), which includes people with severe learning disabilities, our carers group and our co-applicant, Al and staff at Southampton Mencap.

People with learning disabilities described their significant anxieties and fear of hospital care. They felt excluded from decision making and had been asked to sign forms they did not understand. They said staff spoke too fast for them to understand, long waits made them anxious, they were afraid of needles and cannulas after bad experiences. They identified pain management, eating and drinking and vital signs (particularly anxiety/discomfort around the use of blood pressure cuffs) as important research priorities.

Family carers told us that they do all of the basic care but it is difficult to get their concerns taken seriously. They felt they had to take a hands-on approach to care and be available 24-7 as advocates and could be excluded from providing support when their son or daughter had requested it (e.g. during an MRI scan).

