7 SAMPLE AND RECRUITMENT

7.1 Eligibility Criteria

7.1.1 Inclusion criteria

- · Adults with a learning disability (over the age of 18)
- · Receiving inpatient care in the hospital site during the data collection period

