Patients can participate in the research without giving consent for their medical notes to be accessed by the researcher and/or for the researcher to make notes during staff meetings about their care. This will be made clear in discussion and is clear on the information and consent sheets. If consent is given for accessing medical records, or a consultee advises that they can be accessed, brief notes will be taken to outline the treatments and assessments undertaken. These will be used to support the interviews with patients, who may, due to their learning disability, find it difficult to remember the details of their hospital treatment and assessment

At the beginning of each planned data collection session the researcher will check if the person and (if relevant) their carer(s) are happy for her to continue, including a discussion about whether the person feels too unwell to participate in observations or interviews that day or too unwell to continue participating in the study. This will be done in a way appropriate to that person's ability to communicate and understand. If anyone shows signs of not wanting the researcher to carry out the study with them at that time, she will stop collecting data that day. If this happens again the next day, the researcher will withdraw that person from the study completely. If a patient or carer says at any point they don't want to be in the study anymore, or it is their view (or the view of their personal consultee) that the patient does not wish to participate any longer the researcher will withdraw that person from the study completely.

It is possible that existing participants may move onto an End-of-life care pathway or into an Intensive Care Unit. If this happens, we will review their participation with them with the support of their carer or personal consultee if relevant and withdraw them from the study at this point if they wish.

If a participant with a learning disability wishes to withdraw their data from the study, they can do so during the data collection period, but not afterwards. This is made clear on the information sheets and will be discussed with all potential participants.

Carers

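### Does the section 8.4 pause in advisory group meetings conflict with the coding and co-design sessions it schedules from month 9?

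*Protocol*

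**What the plan says.** Section 8.4 says the advisory groups of people with learning disabilities "will meet monthly (except during fieldwork) to ensure they are fully involved". The activity list in the same section then gives "Month 9: Discuss initial findings and develop third order coding" and "Months 9-17: co-design sessions to create outputs".

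The summary of PPI activities in the front matter (roles and responsibilities) covers the same ground with two differences. The exception for the same groups is limited to "the first two months of fieldwork) to ensure they are fully involved", and the last list item reads "Months 9-18: co-design sessions to create outputs". That summary also supplies the fieldwork dates, in its line on co-applicant meetings, which are held "monthly except during the fieldwork phase (March-June 2025".

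On withdrawal, section 7.3.2 gives patients this limit: "withdraw their data from the study, they can do so during the data collection period, but not afterwards". Section 7.1.1 uses the same term for the whole recruitment window: "Receiving inpatient care in the hospital site during the data collection period".

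**The concern.** Taken at face value, section 8.4 cannot be followed in full. If the groups do not meet at any point in fieldwork, the month 9 session cannot be held. If it is held, the meeting rule is broken. The front matter states a different rule for the same groups, and the two places disagree on when co-design ends.

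More than a diary entry could be at stake. Co-design of guidance is the third objective, and whether people with learning disabilities help shape the coding while cases are still being recruited is a question of method.

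The withdrawal rule adds a second worry. If the period in section 7.3.2 is the study-wide four months, material discussed in May and June 2025 could still be withdrawn by a patient, and the protocol gives no rule for codes or draft outputs that have already drawn on it.

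**Working it through.** **Inputs.** Planned study period September 2024 to March 2026 (study summary). Fieldwork March to June 2025 (front-matter PPI summary). Four months of data collection (section 5). Activity months from the two PPI lists. The protocol does not tie month numbers to dates, and the flow chart's shading is not available, so the mapping is inferred from the study start and the chart's first column.

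**Fieldwork in month numbers.** Month number = calendar months elapsed since month 1, plus 1. With September 2024 as month 1:
- March 2025: 6 + 1 = 7. June 2025: 9 + 1 = 10. Fieldwork is months 7 to 10, and 10 − 7 + 1 = 4 months, which reproduces the stated four.
- Month 9 is May 2025, the third fieldwork month.
- Month 17 is January 2026 and month 18 is February 2026. March 2026, the study end, is month 19.

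**Sensitivity to the start month.**

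| Month 1 | Fieldwork | Month 9 | Months 5–6 (ethics committee responses) | Month 18 |
|---|---|---|---|---|
| Sep 2024 | 7–10 | May 2025, inside | Jan–Feb 2025, before fieldwork | Feb 2026 |
| Oct 2024 | 6–9 | Jun 2025, inside | Feb–Mar 2025, runs into fieldwork | Mar 2026 |
| Nov 2024 | 5–8 | Jul 2025, outside | Mar–Apr 2025, inside fieldwork | Apr 2026, after study end |

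A November start is not tenable. September is the only one of the three that places the ethics committee discussions wholly before fieldwork. The literal clash in section 8.4 holds for September and October.

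**Which rule the lists follow.** With month 1 as September, the first two fieldwork months are 7 and 8. The section 8.4 list ends its pre-fieldwork items at month 6, has nothing for 7 and 8, and resumes at 9. The front-matter list has the same gap. The section 8.4 list therefore follows the front-matter rule, not the shorter parenthesis printed above it.

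**Length of co-design.** Section 8.4: 17 − 9 + 1 = 9 months. Front matter: 18 − 9 + 1 = 10 months. The stated difference is 1 month. A larger gap appears only if the full pause is applied to all co-design, giving months 11 to 17, or 7 months. The protocol does not say that: the pause is attached to the learning-disability groups, the carers' group meets on alternate months with no stated pause, and section 4.2 also has outputs developed in workshops with nursing staff.

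**Overlap with withdrawal.** If the period in section 7.3.2 is study-wide, co-design overlaps it in months 9 and 10, which is 2 months (1 month with an October start). If it means the patient's own admission, cases already finished have no overlap.

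**The case for a change.** The best argument for a change is that this is a contradiction in current text, within one section, about the groups whose involvement the study exists to promote. Section 8.5 does not allow planned deviations, so a team following one sentence of section 8.4 departs from another. Data withdrawal is a right that, according to section 7.3.2, the information sheets set out, so its end date ought to be clear. With eight case studies, losing one could matter to the analysis.

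The contradiction in wording stands, as does the 17 versus 18 discrepancy. The rest carries less weight. Section 8.5 frames its bar in terms of clinical trial regulation and takes enrolment of ineligible subjects as its example; the date of an advisory meeting is remote from that. One case is one of eight whenever a patient withdraws, so that fraction does not measure any effect of the schedule. The information sheets are not among the pages available and may define the period.

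Nor does the protocol treat month 9 material as settled. Section 8.4 calls it initial findings and has the workshops check it. Section 5 uses constant comparison and has the case study and ethnographic analyses refined and combined during co-production. Analysing while data are still coming in is normal in that approach. If a patient withdrew data, linked study IDs would let the analyst find and remove the case and revisit the codes that drew on it. A stated rule would be tidier, but analysts in this tradition would do this anyway.

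**Conclusion.** No change to the plan follows. The section 8.4 parenthesis is a clerical slip: the activity list beneath it and the front-matter summary agree on a pause in months 7 and 8 and a restart in month 9. The end of co-design differs by one stated month (9 versus 10 months in length), and either end date falls before the planned study end in March 2026. Settling both would move no session and would leave recruitment, consent, data collection and analysis as they are.

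The withdrawal point is missing detail, not an error. It arises only on the study-wide reading of section 7.3.2, for at most two months, and the iterative analysis largely covers it.

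This rests on month 1 being September 2024, which is inferred. With an October start the month 9 session still falls in fieldwork, but the lists fit the two-month pause less neatly, because the ethics committee item would run into March 2025. The conclusion would be the same, since the session dates themselves would not need to move.

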8.5 Protocol compliance

The Investigator agrees to comply with the requirements of the Protocol and Good Clinical Practice. Prospective, planned deviations or waivers to the protocol are not allowed under the UK regulations on Clinical Trials and must not be used e.g. it is not acceptable to enrol a subject if they do not meet the eligibility criteria or restrictions specified in the trial protocol.

Accidental protocol deviations can happen at any time. They must be adequately documented on the relevant forms and reported to the Chief Investigator and Sponsor immediately.

Deviations from the protocol, which are found to frequently recur, are not acceptable and will require immediate action by the sponsor. Frequent non-compliances could potentially be classified as a serious breach

